## **7.3 Expedited Adverse Event Reporting**

- 7.3.1 Expedited AE reporting for this study must use CTEP-AERS, accessed via the CTEP home page (<http://ctep.cancer.gov>). The reporting procedures to be followed are presented in the “CTEP, NCI Guidelines: Adverse Event Reporting Requirements” which can be downloaded from the CTEP home page

(<http://ctep.cancer.gov>). These requirements are briefly outlined in the [table](#) below ([Section 7.3.3](#)).

A 24-hour notification is to be made to the AMC by telephone at [contact], only when Internet connectivity is disrupted. Once Internet connectivity is restored, a 24-hour notification phoned in must be entered electronically into CTEP-AERS by the original submitter at the site.

7.3.2 CTEP-AERS is programmed for automatic electronic distribution of reports to the following individuals: Study Coordinator of the Lead Organization, Principal Investigator, and the local treating physician. CTEP-AERS provides a copy feature for other email recipients.

7.3.3 Expedited reporting guidelines

Use the NCI protocol number and the protocol-specific patient ID assigned during trial registration on all reports.

Note: A death on study requires both routine and expedited reporting regardless of causality, unless as noted below. Attribution to treatment or other cause must be provided.

Death due to progressive disease should be reported as **Grade 5 “General disorders and administration site conditions – Disease Progression”**. Evidence that the death was a manifestation of underlying disease (e.g., radiological changes suggesting tumor growth or progression: clinical deterioration associated with a disease process) should be submitted.

## FOR USE IN CIP STUDIES INVOLVING COMMERCIAL (NON-IND/IDE) AGENTS ONLY

### CIP Commercial Agent Studies: Expedited Reporting Requirements for Adverse Events that Occur in a CIP Non-IND/IDE trial within 30 Days of the Last Administration of a Commercial Imaging Agent

#### FDA REPORTING REQUIREMENTS FOR SERIOUS ADVERSE EVENTS (21 CFR Part 312)

**NOTE:** Investigators **MUST** immediately report to the sponsor (NCI) **ANY** Serious Adverse Events, whether or not they are considered related to the investigational agent(s)/intervention (21 CFR 312.64)

An adverse event is considered serious if it results in **ANY** of the following outcomes:

- Death
- A life-threatening adverse event
- An adverse event that results in inpatient hospitalization or prolongation of existing hospitalization for  $\geq$  24 hours
- A persistent or significant incapacity or substantial disruption of the ability to conduct normal life functions
- A congenital anomaly/birth defect.

Important Medical Events (IME) that may not result in death, be life threatening, or require hospitalization may be considered serious when, based upon medical judgment, they may jeopardize the patient or subject and may require medical or surgical intervention to prevent one of the outcomes listed in this definition. (FDA, 21 CFR 312.32; ICH E2A and ICH E6).

**ALL SERIOUS** adverse events that meet the above criteria **MUST** be immediately reported to the NCI via CTEP-AERS within the timeframes detailed in the table below.

Hospitalization	Grade 1 Timeframes	Grade 2 Timeframes	Grade 3 Timeframes	Grade 4 & 5 Timeframes
Resulting in Hospitalization $\geq$ 24 hrs		10 Calendar Days		24-Hour 5 Calendar Days
Not resulting in Hospitalization $\geq$ 24 hrs	Not required		10 Calendar Days	

**NOTE:** Protocol specific exceptions to expedited reporting of serious adverse events are found in the Specific Protocol Exceptions to Expedited Reporting (SPEER) portion of the CAEPR

Expedited AE reporting timelines are defined as:

- “24-Hour; 5 Calendar Days” - The AE must initially be reported via CTEP-AERS within 24 hours of learning of the AE, followed by a complete expedited report within 5 calendar days of the initial 24-hour report.
- “10 Calendar Days” - A complete expedited report on the AE must be submitted within 10 calendar days of learning of the AE.

Serious adverse events that occur more than 30 days after the last administration of investigational agent/intervention and have an attribution of possible, probable, or definite require reporting as follows:

Expedited 24-hour notification followed by complete report within 5 calendar days for:

- All Grade 4, and Grade 5 AEs

Expedited 10 calendar day reports for:

- Grade 2 adverse events resulting in hospitalization or prolongation of hospitalization
- Grade 3 adverse events

 For studies using PET or SPECT agents, the AE reporting period is limited to 10 radioactive half-lives, rounded UP to the nearest whole day, after the agent/intervention was last administered. Footnote “1” above applies after this reporting period.

*Effective Date: May 5, 2011*

## 7.4 Routine AE Reporting

All Grade 3 or greater AEs, whether or not ascribed to the study drug administration, will be recorded on the Adverse Event Form. Unexpected Grade 1 and 2 AEs that are considered to be related to study drug administration will be captured on the AMC Adverse Event Form. Expected Grade 1 and 2 AEs that are related to study drug administration will be captured on the Expected Toxicity form, and do not require reporting in the Adverse Event form. Grade 1 and 2 adverse events that are not considered related to study drug administration will not require reporting for this protocol. These requirements are summarized in the chart below.

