## PROTOCOL SYNOPSIS

Title:	A Randomized, Phase III Study of Intra-anal Imiquimod 2.5% vs. Topical 5-fluorouracil 5% vs. Observation for the Treatment of High-grade Anal Squamous Intraepithelial Lesions (HSIL) in HIV-positive Men and Women
Phase of Study:	Phase III
Study Design:	Prospective, randomized, three-arm, open-label study to evaluate the complete response rate of intra-anal high-grade squamous intraepithelial lesions (HSIL) treated with imiquimod 2.5% or topical 5-fluorouracil 5% (5FU) as compared to spontaneous regression in human immunodeficiency virus (HIV)-infected participants.  As of protocol version 5.0, the imiquimod 2.5% arm was dropped because of product unavailability.
	At randomization, participants will be randomized to intra-anal topical 5FU or observation. Participants will be followed with anal cytology and anoscopy without biopsy through 16 weeks of treatment or observation. At Week 20 (four weeks after completing randomized treatment), high-resolution anoscopy (HRA) with biopsies and cytology will be performed for the primary endpoint. Participants originally assigned to the observation arm having anal HSIL at Week 20 will be offered 5FU for 16 weeks (Weeks 24-40). Participants originally assigned 5FU with anal HSIL at Week 20 will be referred for treatment off study according to the local standard of care. All participants will be seen at Week 44 for HRA with biopsies of visible lesions.
Accrual Target:	88 participants
Population:	HIV-infected participants with biopsy-proven high-grade anal intraepithelial lesions (AIN; AIN2 with positive p16 stain, AIN2-3, or AIN3).
Regimen:	

• Arm A: Imiquimod 2.5% cream applied to the intra-anus daily for 16 weeks. Perianal disease will also be treated if present. Closed as of protocol version 5.0.

• Arm B: Topical 5FU cream to the intra-anus twice daily for five days followed by nine days off. This cycle is repeated eight times over 16 weeks. Perianal disease will also be treated if present.

• Arm C: No treatment is given for 16 weeks.

Duration of Participation:	44 weeks

Primary Objective:	Complete response is defined as no anal biopsies with HSIL and cytology without HSIL at Week 20.

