#### 6.4 Visit 3 (Week 8) +/- 14 days

6.4.1 The following evaluations will be performed, and laboratory samples will be collected for all participants:

- Clinical assessment: The participant's medical history will be updated for any changes. A review of systems for any new or changed local symptoms, such as hematochezia, dyschezia, erythema, swelling, or pruritus. A targeted physical exam should be performed as indicated (see [Section 6.2.1](#)).
- Pregnancy test: Urine or serum beta-HCG will be performed (and results obtained) when indicated (women of childbearing potential).
- Anal swab for HPV testing.
- For study participants randomized to the 5-fluorouracil 5% arm only: HRA will be performed provided that the participant is not experiencing significant anal discomfort from the study treatment. In such a case, anoscopy should be performed without soaking the anal canal with acetic acid. Acetic acid and/or Lugol's solution should only be used sparingly to avoid further participant discomfort. The number of involved octants, location, and percent circumference of HSIL will be documented. Anal biopsies should be performed only if the clinician notes suspicious friability, ulceration, mass effect, heaped-up borders, and/or markedly abnormal vascular pattern. This could be indicative of progression of the lesion toward invasive disease.
- HRA may be performed in the observation arm if disease progression is suspected.
- If performing HRA, all lesions, all aspects of the anal transformation zone, distal canal and perianus will be photographically documented.
- Collect study diary and evaluate treatment adherence. Additional instruction on proper administration of study treatment should be given as needed. Partially used containers should be weighed to measure the amount of cream used. Participants will receive new replacement containers as needed for their

appropriate study arm. Study agent must be weighed prior to distribution to the participant to allow for accurate measurement of adherence.

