## **7.2 Classification of AEs by Severity and Relationship to Study Drug Administration**

- 7.2.1 Adverse Event: Any unfavorable and unintended sign (including an abnormal laboratory finding), symptom or disease temporally associated with the use of a medical treatment or procedure regardless of whether it is considered related to the medical treatment or procedure (attribution of unrelated, unlikely, possible, probable, or definite).
- 7.2.2 Life-threatening Adverse Event: Any AE that places the subject or subject, in view of the Investigator, at immediate risk of death from the reaction.
- 7.2.3 Serious Adverse Event (SAE): Any AE occurring at any dose that results in any of the following outcomes: Death, a life-threatening AE, inpatient hospitalization or prolongation of existing hospitalization, a persistent or significant disability/incapacity, or a congenital anomaly/birth defect.
- 7.2.4 Please note for hospitalization – All hospitalizations (or prolongation of existing hospitalization) for medical events equivalent to CTCAE Grade 3, 4, 5 must be reported regardless of the requirements for Phase of study, expected or unexpected, and attribution. For example, do not report an admission for pharmacokinetic sampling, but do report an admission for a myocardial infarction.
- 7.2.5 Toxicity: Toxicity is a term NOT clearly defined by regulatory organizations. Toxicity has been described as an AE that has an attribution of possibly, probably or definitely related to investigational treatment. To minimize confusion the NCI would recommend that the term toxicity NOT be utilized for AE reporting purposes. The CTCAE continues to use the term ‘toxicity’ because of familiarity.
- 7.2.6 Unexpected Adverse Event: Any AE that is not listed in available sources including the package insert, the Investigator’s Brochure, or the protocol.
- 7.2.7 Cancer Therapy Evaluation Program Adverse Event Reporting System (CTEP-AERS): An electronic system for expedited submission of AE reports.
- 7.2.8 Attribution: The determination of whether an AE is related to a medical treatment or procedure. Attribution categories:
  - Definite – The AE is clearly related to the investigational agent.
  - Probable – The AE is likely related to the investigational agent.
  - Possible – The AE may be related to the investigational agent.
  - Unlikely – The AE is doubtfully related to the investigational agent.
  - Unrelated – The AE is clearly NOT related to the investigational agent.

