### **10.5 Safety Analysis**

AEs will be summarized at the event level and participant level according to severity. Proportions and their exact 95% confidence intervals will be calculated.

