## 10.8 Secondary Analyses

To examine the tolerability and safety of the three arms, descriptive statistics for AEs will be computed. AEs will be summarized at the event level and subject level according to severity. AEs will be stratified according to those reported at or before Week 20 and after Week 20 since those in the observation arm have to option of being randomized to imiquimod or 5FU at Week 20. Proportions and their exact binomial 95% confidence intervals will be calculated. We will compute summary statistics for the amount of study drug taken by measuring the mass of study drug dispensed (weight of study drug container at baseline – weight of study drug at the end of treatment).

Similarly, we will assess for PR in two ways. We will compare between arms the number of quadrants with HSIL found on biopsies treating the response as an ordinal variable. The biopsy plan for Week 20 and 48 (see [Appendix V](#)) specifies that at least one biopsy be obtained from each quadrant. Biopsies used for eligibility will generally be obtained through routine care and will not necessarily have four quadrant biopsies, so we are not able to look at the within participant change in the number of quadrants with HSIL on biopsy. Therefore, this comparison between arms assumes that the extent of disease at enrollment is balanced between arms, which is reasonable given randomization. We will also compare the proportion of participants achieving CR or PR (as per [Section 9](#)) with imiquimod or 5FU as compared to observation only using similar approaches as the primary objective.

We will evaluate the effect of imiquimod and 5FU on persistence of HPV type specific infections. We will report the frequency and proportion of HPV types present at baseline that are no longer detected at Week 20. We will also report the frequency and proportion of new HPV infections detected at Week 20 that were not present at baseline. Proportions and their exact binomial 95% confidence intervals will be calculated.

HSIL outcomes at Week 44 will be analyzed similarly to those at Week 20. Results for the observation arm will be stratified into cross-over treatment groups.

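### Grade 1-2 adverse events are in effect not collected in the observation arm before cross-over, yet the plan would tabulate them there with an exact confidence interval

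*Combined protocol and SAP*

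**What the plan says.** Section 7.4 sets two recording rules. For the higher grades, "All Grade 3 or greater AEs, whether or not ascribed to the study drug administration, will be recorded on the Adverse Event Form". For the lower grades, "Grade 1 and 2 adverse events that are not considered related to study drug administration will not require reporting for this protocol". Table 7-A repeats this, with related meaning an attribution of possible, probable or definite. Section 7.2.8 words all five attribution categories against the agent. The lowest one that triggers a Grade 1-2 record reads "The AE may be related to the investigational agent".

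The Synopsis says of the observation arm: "Arm C: No treatment is given for 16 weeks". Observation participants who still have HSIL at Week 20 may then take 5FU from Week 24.

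On analysis, Section 10.8 says "To examine the tolerability and safety of the three arms, descriptive statistics for AEs will be computed". It splits events at Week 20 and attaches exact binomial 95% intervals to the proportions. Section 10.5 adds "AEs will be summarized at the event level and participant level according to severity", also with exact intervals but without mentioning arms. Section 10.4 defines the safety population as everyone randomized. Neither 10.5 nor 10.8 restricts the low-grade rows to treated participants or says how the observation cells should be shown.

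**The concern.** Recording of a Grade 1-2 event depends on attribution to a drug that the observation arm does not receive before cross-over. The symptoms may well occur there. At Week 8 (Section 6.4.1) every participant, treated or not, has "A review of systems for any new or changed local symptoms", and Section 6.1.1 expects problems such as hemorrhoids, fissure, pruritus and pain to be present at screening. A mild symptom reported by an observation participant simply need not be entered as an adverse event.

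A table built from Section 10.8 would therefore set a rate of drug-attributed events on 5FU beside a near-zero that comes from the recording rule. Safety and tolerability are a secondary objective (Section 2.2), and Section 7.1.3 expects most 5FU effects to be local, so the low-grade rows are likely to be read closely. A zero with a confidence interval looks like an observed absence of symptoms.

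**Working it through.** The documents give no Grade 1-2 rate, so there is no stated figure to reproduce. The planned denominators in Section 10.1 do reconcile: 35 (5FU) + 35 (observation) + 18 (imiquimod) = 88.

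**Step 1: the observation cell up to Week 20.** Routine Grade 1-2 recording needs a drug attribution, and there is no drug exposure in this arm, so the expected entry is about 0 of 35. The exact 95% upper limit for 0/35 is 1 - 0.025^(1/35) = 10.0%, so the table would print 0% (0% to 10.0%).

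**Step 2: what full collection would have shown.** Let b be the background risk of at least one Grade 1-2 event. This is an assumption; the documents give no value. The expected observation counts are 35 × 0.10 = 3.5 and 35 × 0.20 = 7. If the data had been collected and b were 20%, the probability of a genuine 0/35 would be 0.8^35 = 0.0004.

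**Step 3: the arm difference a reader would infer.** Further inputs:
- d, the risk of a 5FU-caused Grade 1-2 event. For illustration d = 48%, the share with moderate to severe side effects in an earlier open-label study cited in Section 1.1.1. That study used a different regimen and grading.
- s, the share of drug-caused events attributed to drug (assumption).
- m, the share of background events on 5FU attributed to drug (assumption).

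Taking drug-caused and background events as independent:
- True all-cause difference = [1 - (1 - b)(1 - d)] - b = d(1 - b). This is 0.48 × 0.90 = 43.2 points at b = 10%, and 0.48 × 0.80 = 38.4 points at b = 20%.
- Recorded difference = 1 - (1 - ds)(1 - bm) - 0.

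| Attribution on 5FU | Recorded, b = 10% | Bias | Recorded, b = 20% | Bias |
|---|---|---|---|---|
| Accurate (s = 1, m = 0) | 48.0 | +4.8 | 48.0 | +9.6 |
| Every background event attributed (s = 1, m = 1) | 53.2 | +10.0 | 58.4 | +20.0 |
| Strict (s = 0.8, m = 0) | 38.4 | -4.8 | 38.4 | 0.0 |
| Stricter (s = 0.6, m = 0) | 28.8 | -14.4 | 28.8 | -9.6 |

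The first two rows simplify to a bias of d × b and of b. With d = 73% (any irritation in another small study cited in Section 1.1.1, also on a different schedule), accurate attribution gives 0.73 × 0.10 = +7.3 and 0.73 × 0.20 = +14.6 points.

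**Step 4: event counts.** Under accurate attribution, recorded 5FU events minus zero equals the drug-caused excess, so event-level counts carry no bias. The distortion is in participant-level proportions and in the interval around the empty cell.

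**Step 5: after Week 20.** Only observation participants who cross over can contribute drug-attributed low-grade events. Section 10.8 states a split by cross-over group for HSIL outcomes but not for adverse events.

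**The case against.** The strongest reply is that the plan never estimates a 5FU excess. Section 10.8 is descriptive, with single-arm intervals and no risk difference or test. The safety objective in Section 2.2 names the two drugs and no comparator, whereas the partial-response objective does name observation. Recording only drug-related low-grade events is a legitimate design choice, and attributed rates in treated participants answer the objective as written. All of this stands, and it confines the point to presentation. It does not rescue the observation cell, because Section 10.8 names three arms and Section 10.4 puts untreated participants in the denominator.

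Four stronger readings are tempting, and the documents do not support them.
- A reader might infer a flat overstatement of 10-20 points. That requires every background event on 5FU to be called drug-related. The rule drops unrelated low-grade events on 5FU too, and strict attribution can reverse the sign.
- A reader might take biopsy-site bleeding as the background event. Section 7.1.1 limits it to about a week, eligibility biopsies precede randomization by at least seven days (Section 3.1.2), and the Week 20 biopsies come at least two weeks after the last dose (Section 6.6). Routine biopsies barely overlap dosing.
- A reader might infer that low-grade observation events can never appear. Section 7.4 does not require them, which is not a prohibition, and Section 7.3.3 covers serious events whatever their attribution.
- A reader might infer that Grade 3 and above is captured identically across arms. The reporting rule is the same, but the Week 2 visit (Section 6.3) and the diary are for treated participants, and routine HRA at Week 8 is for 5FU only (Section 6.4.1).

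Changing data collection now is not worthwhile. Enrollment closed on 1 July 2023 at about one participant per month. Twenty weeks is about 4.6 months, so at most about five participants would still have been before Week 20, and two recording rules would be mixed in one table.

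**Conclusion.** The point holds in a limited form. For routinely reported Grade 1-2 events before cross-over, the observation arm is essentially empty because of the recording rule, and the plan would print about 0/35 (0% to 10.0%) for events that were not collected. Any-grade rows inherit the defect; Grade 3 and above rows do not, as far as the reporting rule goes.

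Overstatement of the participant-level 5FU excess is likely, because the trial is open-label and attribution is made knowing the arm. It is not certain. At assumed background risks of 10-20% and d = 48%, the bias runs from -14.4 to +20 points depending on attribution, and the collected data cannot show where in that range it falls. The illustration rests on the assumed b, s and m, on a d borrowed from a different regimen, and on the planned denominators of 35. Efficacy results and error rates are untouched.

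**What to change.** In Sections 10.5 and 10.8:
- Limit by-arm adverse event tables to Grade 3 and above, where one reporting rule applies to all arms, with a footnote that visit and diary intensity differs between treated and untreated participants.
- Report Grade 1-2 events only for participants while on study drug, including observation participants after cross-over, and label them as drug-attributed events.
- Mark Grade 1-2 and any-grade cells for untreated observation participants as not collected, with no proportion and no confidence interval.

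The cost is a change to table shells and a few sentences in the analysis section. No new data are needed.

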**Table 7-A: Routine AE reporting requirements by grade and relationship to study agents**

Relationship to Study Agents	Grade 1 or 2	Grades 3, 4, or 5
Unrelated ( attribution of unrelated or unlikely )	Not Required	Adverse Event Form
Related ( attribution of possible, probable, or definite )	Expected: Expected Toxicity Form Unexpected: Adverse Event Form	Adverse Event Form

Participants withdrawn from the study due to AEs will be followed by the Investigator until the outcome is determined and, when appropriate, additional written reports and documentation will be provided.

